1688 1689 1690 1691	The participants may withdraw consent at any time throughout the course of the trial. A copy of the informed consent document will be given to the participants for their records. The rights and welfare of the participants will be protected by emphasizing to them that the quality of their medical care will not be adversely affected if they decline to participate in this study.
1692	This process shall be document in the study records at each site (e.g., consent process note).
1693	13.3.2 Participant and Data Confidentiality
1694 1695 1696 1697 1698 1699	Participant confidentiality is strictly held in trust by the participating investigators, their staff, and the sponsor(s) and their agents. This confidentiality is extended to cover testing of biological samples and genetic tests in addition to the clinical information relating to participants. Therefore, the study protocol, documentation, data, and all other information generated will be held in strict confidence. No information concerning the study or the data will be released to any unauthorized third party without prior written approval of the sponsor.

- 1700 The study monitor, other authorized representatives of the sponsor, representatives of the IRB,
- regulatory agencies or company supplying study product may inspect all documents and records
- required to be maintained by the investigator, including but not limited to, medical records
- 1703 (office, clinic, or hospital) and pharmacy records for the participants in this study. The clinical
- study site will permit access to such records.
- 1705 The study participant's contact information will be securely stored at each clinical site for
- internal use during the study. At the end of the study, all records will continue to be kept in a
- secure location for as long a period as dictated by the reviewing IRB, institutional policies, or
- sponsor requirements.
- 1709 Study participant research data, which is for purposes of statistical analysis and scientific
- 1710 reporting, will be transmitted to and stored at the Jaeb Center for Health Research (JCHR). This
- will not include the participant's contact or identifying information, unless otherwise specified in
- the informed consent form. Rather, individual participants and their research data will be
- identified by a unique study identification number. The study data entry and study management

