- 473 randomization will not be stratified by age, HbA1c or other factors because of the small number
- *per site that is possible and considering the 2:1 randomization.*

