1323 1324 1325 1326 1327 1328	HbA1c data from N=30 participants in the 2IQ pilot study were used to estimate the SD for the power calculation. The SD for baseline values was 1.0%. Assuming a similar SD at follow-up, correlation of 0.3 with baseline, and a two-sided test with type 1 error at 5%, a sample size of N=300 completers will be able to detect an HbA1c difference as small as 0.38% with 90% power. There will be 85% power to detect a difference of 0.35% and 80% power for a difference of 0.33%.
1329	11.4 Efficacy Outcome Measures
1330	11.4.1 Primary Efficacy Endpoint
1331	• HbA1c at 13 weeks (superiority)

1332	11.4.2 Secondary Efficacy Endpoints Included in Hierarchical Analysis
1333 1334	The following secondary endpoints will be tested for superiority, with a hierarchical testing approach to protect the type 1 error rate as described in section 11.13.
1335	• Time in range 70-180 mg/dL
1336	Mean glucose
1337	• Time $> 180 \text{ mg/dL}$
1338	• Time $>$ 250 mg/dL
1339	• CGM-measured prolonged hyperglycemia events (defined in section 11.7.1)
1340	• Time <70 mg/dL
1341	• Time <54 mg/dL
1342	CGM-measured hypoglycemia events (defined in section 11.7.1)
1343	• Coefficient of variation
1344	
1345	11.4.3 Other Secondary Efficacy Endpoints
1346 1347	The following efficacy endpoints are considered exploratory as they are not included in the overall type 1 error rate. All statistical tests are for superiority.
1348	Binary HbA1c Endpoints:
1349	HbA1c <7.0% at 13 weeks
1350	HbA1c <7.0% at 13 weeks in participants with baseline HbA1c >7.5%
1351	HbA1c <7.5% at 13 weeks
1352	HbA1c improvement from baseline to 13 weeks >0.5%
1353	HbA1c improvement from baseline to 13 weeks >1.0%
1354	HbA1c relative improvement from baseline to 13 weeks >10%
1355	HbA1c improvement from baseline to 13 weeks >1.0% or HbA1c <7.0% at 13 weeks
1356	Continuous CGM-Measured Endpoints:
1357	Time in range 70-140 mg/dL
1358	Area over the curve (70 mg/dL)
1359	Low blood glucose index
1360	Time $>$ 300 mg/dL
1361	Area under the curve (180 mg/dL)
1362	High blood glucose index
1363	Binary CGM-Measure Endpoints
1364	Time in range 70-180 mg/dL $>$ 70%
1365	Time in range 70-180 mg/dL improvement from baseline to 13 weeks ≥5%

1366	Time in range 70-180 mg/dL improvement from baseline to 13 weeks \geq 10%
1367	Time $<$ 70 mg/dL $<$ 4%
1368	Time <54 mg/dL $<1\%$
1369	Time in range 70-180 mg/dL $>$ 70% and time $<$ 54 mg/dL $<$ 1%
1370	Other Endpoints (analyzed for superiority as continuous variables):

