11.6 Analysis of the Primary Efficacy Endpoint: HbA1c

- HbA1c at 13 weeks will be compared between the AID and Control Groups using a linear mixed
- effects regression model adjusting for baseline HbA1c and clinical center (random factor). A
- separate variance will be modelled for each treatment group. HbA1c is expected to be normally
- distributed, but regression diagnostics will be performed to check the residuals and an
- appropriate alternative transformation or robust statistical method (e.g., non-parametric or MM
- estimation) will be performed if the residuals have a skewed distribution. In the event that some
- 1433 HbA1c values are not available at 13 weeks, then the linear mixed effect regression model will
- 1434 use the method of direct likelihood to incorporate information from baseline measurements to
- calculate the maximum likelihood at 13 weeks. Only central lab HbA1c measurements will be
- used in the analyses. Imbalances between groups in important covariates are not expected to be
- of sufficient magnitude to produce confounding. However, the presence of confounding will be
- of sufficient magnitude to produce combanding. However, the presence of combanding will be
- evaluated in the sensitivity analyses by including factors potentially associated with the outcome
- 1439 for which there is an imbalance between groups (11.5.2).

1440	11.7 Analysis of Secondary Endpoints
1441	11.7.1 CGM Metrics
1442 1443 1444	Baseline values for each CGM metric will be computed from 14 days of CGM data prior to randomization. A minimum of 72 hours of CGM data will be required to calculate baseline metrics.
1445 1446	CGM data starting from randomization visit through the 13-week visit will be included in the calculation of each CGM metric for each participant, giving equal weight to each CGM point.
1447 1448 1449 1450 1451	Calculation of CGM metrics for the treatment group comparisons will exclude the challenges and the period through 6 AM on the day following the end of the challenge. CGM metrics during and following the challenges will be reported separately as described in section 11.15.3 and an overall analysis within the AID group will be performed for all CGM data including the challenge data as described in section 11.15.2.

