### 395 7. Primary Analyses

396

397 The primary endpoint for this study is HbA1c at 13 weeks adjusted for baseline HbA1c.

Summary statistics (mean  $\pm$  SD or median (quartiles) – appropriate to the distribution) will be reported for the baseline, 13 weeks values, and their differences.

HbA1c at 13 weeks will be compared between the AID and Control Groups using a linear mixed effects
regression model adjusting for baseline HbA1c and clinical center (random factor). A separate variance
will be modelled for each treatment group. HbA1c is expected to be normally distributed, but regression
diagnostics will be performed to check the residuals and an appropriate alternative transformation or
robust statistical method (e.g., non-parametric or M-estimation) will be performed if the residuals have a
skewed distribution.

In the event that some HbA1c values are not available at 13 weeks then the linear mixed effect
regression model will use the method of direct likelihood to incorporate information from baseline
measurements to calculate the maximum likelihood at 13 weeks. The method of direct likelihood will
function similarly in the event of missing HbA1c at baseline for a participant.

410 Only central lab HbA1c measurements will be used in the analyses.

411 Imbalances between groups in important covariates are not expected to be of sufficient magnitude to

412 produce confounding. However, the presence of confounding will be evaluated in the sensitivity

- analyses by including factors potentially associated with the outcome for which there is an imbalance
- 414 between groups (see Section 8.4 below).
- 415
- 416
- 417

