#### 476 **8.4. Sensitivity Analyses**

477 Confounding

A sensitivity analysis for the primary outcome, HbA1c, will also be conducted if potential confounding
factors collected at baseline are detected.

- The imbalance will be assessed based on clinical judgment reviewing the distributions in the two
  treatment arms, not on a p-value. The person making this judgement will be unaware of whether there is
  an association between baseline variables and study outcome.
- 483
- 484 Missing Data
- 485 Missing data will be handled using direct likelihood method for the primary analysis. It is worth noting 486 that all statistical methods for handling missing data rely on untestable assumptions and there is no one 487 correct way to handle missing data. Our goal is to minimize the amount of missing data so that the 488 results will not be sensitive to which statistical method is used.
- To that end, sensitivity analyses will be performed to explore whether results are similar for primaryanalysis when using different methods. The following methods will be applied:
  - Rubin's multiple imputation with treatment group in the imputation model
  - Available cases only
- Multiple imputation with pattern mixture model assuming the dropout trajectory of the AID group was that of the Control group (Mallinckrodt and Clark, 2003)
- Tipping point analysis to determine the magnitude of selective dropout bias necessary to alter conclusions of the study.
- 497

491

492

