## 13. Baseline Descriptive Statistics

Baseline demographic and clinical characteristics of the randomized cohort will be summarized by
 treatment group in a table using summary statistics appropriate to the distribution of each variable.
 Descriptive statistics will include the following:

595	• Age						
596	• Sex						
597	• Race/Ethnicity						
598	Diabetes duration						
599	• Insulin method before enrollment (basal only or multiple daily injections)						
600	CGM use before enrollment						
601	• HbA1c						
602	• BMI						
603	• C-Peptide						
604	GAD Antibody						
605	Total daily insulin						
606	Non-insulin glucose-lowering medications						
607	• SH, DKA, and HHS episodes during the previous 12 months						
608	CHF hospital admissions during the last 12 months						
609	
 
Non-Severe SH episodes during the previous 3 months
 
						
610							
611							
612	14. Planned Interim Analyses						
613							
614	No formal interim efficacy analyses are planned for this study.						
615							
616	The DSMB will review safety data at intervals, with no formal stopping rules other than the guidelines						
017 619	provided in the participant-level and study-level stopping criteria in the Protocol.						
619	The medical monitor will review all cases of severe hypoglycemia and diabetic ketoacidosis irrespective						
620	of device relationship all device related SAEs and all UADEs at the time that they occur during the						
621	study and will review compiled safety data at periodic intervals.						
622							
622							
623	15. Subgroup Analyses						
624							
625	In exploratory analyses, the primary outcome (HbA1c) and time in range 70-180 mg/dL will be						
626	compared in baseline subgroups. Treatment group by subgroup factor interaction terms will be added to						

- 627 the linear models described above.
- 628

Formal tests will be done only if the overall result is statistically significant. Results will be tabulated by 629 subgroups regardless of statistical significance. For continuous variables, results will be displayed in 630 subgroups based on cutpoints although the analysis will utilize the variable as continuous. If there is 631 632 insufficient sample size in a given subgroup, the cutpoints for continuous measures may be adjusted per the observed distribution of values. Cutpoint selection for display purposes will be made masked to the 633 outcome data

634

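### Three baseline variables already collected could be prespecified in the primary HbA1c model; the gain in precision may be negligible or material

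*Protocol*

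**What the plan says.** **Primary model.** Protocol 11.6 specifies a linear mixed "effects regression model adjusting for baseline HbA1c and clinical center (random factor"), with a separate variance for each group. SAP 7 agrees: "regression model adjusting for baseline HbA1c and clinical center (random factor").

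**Other baseline factors.** Protocol 11.5.2 and SAP 8.4 add them only in a sensitivity analysis, when someone judges that the groups differ: "The imbalance will be assessed based on clinical judgment reviewing the distributions in the two" arms. The person judging must not know whether the variables are associated with the outcome. SAP 15 also uses baseline time in range, and prior CGM and pump use, as factors in exploratory interaction models for HbA1c.

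**What is collected.** CGM metrics come from 14 days before randomization (Protocol 11.7.1, SAP 5.3). SAP 13 lists CGM use before enrollment and "Insulin method before enrollment (basal only or multiple daily injections").

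**Randomization.** Blocks are formed within each centre, and "randomization will not be stratified by age, HbA1c or other factors" (Protocol 4.3). The reasons given are the small numbers per site and the 2:1 allocation.

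**Planning values.** Protocol 11.3 states: "The SD for baseline values was 1.0"%, with the same SD assumed at follow-up, "correlation of 0.3 with baseline", and "a two-sided test with type 1 error at 5"%.

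**The concern.** At the planning correlation, baseline HbA1c explains 0.3² = 9% of the variance in the outcome, so 91% is left for other predictors. Three candidates are already in the database, and the SAP already plans to put two of them, plus a baseline CGM metric, into HbA1c models for exploratory purposes. If they predict 13-week HbA1c beyond baseline HbA1c, leaving them out makes the confidence interval for the primary effect wider than it need be. In a linear model without interactions, adding them leaves the target of estimation, the mean difference between groups, unchanged.

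The reason given for not stratifying is the small number per site. It does not apply to adjustment in the model, where site size is no obstacle.

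The SAP 13 categories are a separate matter. Protocol 2.2.1 (criterion 4) admits people on basal-bolus therapy or a pump. SAP 13 offers basal only, which is not an eligible regimen, and has no pump category.

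**Working it through.** **Inputs.** SD 1.0, correlation r = 0.3, two-sided alpha 0.05 and 300 completers (Protocol 11.3; SAP 4). Allocation 2:1 (Protocol 4.3), so 200:100. The partial R² of the added covariates is not in the documents and is varied. A common residual SD is assumed for both groups.

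**Step 1: reproduce the plan's figures.**
- Residual SD = 1.0 × √(1 − 0.3²) = 0.954.
- Standard error of the difference = 0.954 × √(1/200 + 1/100) = 0.954 × 0.1225 = 0.1168.
- Detectable difference = (1.960 + z for power) × 0.1168:
  - 90% power: 3.242 × 0.1168 = 0.379 (plan: 0.38)
  - 85% power: 2.996 × 0.1168 = 0.350 (plan: 0.35)
  - 80% power: 2.802 × 0.1168 = 0.327 (plan: 0.33)
- Power at 0.38, 0.35 and 0.33 is 90.2%, 85.0% and 80.6%. Without adjustment (SD 1.0) it would be 87.3%, 81.5% and 76.9%.

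The plan's figures therefore hold, and they already take credit for adjustment for baseline HbA1c.

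**Step 2: add covariates.** Residual SD = 0.954 × √(1 − partial R²).

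| Assumed partial R² | Residual SD | Detectable at 90% power | Power at 0.38 | Power at 0.33 | Completers needed for 0.38 at 90% |
|---|---|---|---|---|---|
| 0 | 0.954 | 0.379 | 90.2% | 80.6% | 300 |
| 0.02 | 0.944 | 0.375 | 90.8% | 81.4% | 294 |
| 0.05 | 0.930 | 0.369 | 91.6% | 82.6% | 285 |
| 0.10 | 0.905 | 0.359 | 92.9% | 84.6% | 270 |
| 0.20 | 0.853 | 0.339 | 95.3% | 88.5% | 240 |

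If the three terms carry no information, the cost is roughly 3/300 = 1% in variance, or about 0.5% in the standard error.

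**Step 3: which row is plausible for baseline mean glucose alone?** Let c be its correlation with baseline HbA1c and q its correlation with 13-week HbA1c (both assumed). Then R² = (r² + q² − 2rqc)/(1 − c²), and partial R² = (R² − 0.09)/0.91.
- c = 0.8, q = 0.3: R² = (0.09 + 0.09 − 0.144)/0.36 = 0.100; partial R² = 0.011.
- c = 0.8, q = 0.4: R² = (0.09 + 0.16 − 0.192)/0.36 = 0.161; partial R² = 0.078.
- For c from 0.6 to 0.9, q = 0.3 gives 0.005 to 0.025; q from 0.4 to 0.5 gives 0.078 to 0.306.

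If mean glucose predicts no better than baseline HbA1c, the gain is about one power point or less. It becomes material only if mean glucose predicts clearly better.

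**Step 4: if r itself is higher.** At r = 0.5 the residual SD is √(1 − 0.25) = 0.866 and the planned model already detects 3.242 × 0.866 × 0.1225 = 0.344 with 90% power.

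**The case against.** The strongest reply is that nothing here is wrong. The model is fully prespecified, identical in both documents, and gives a valid test. The stated power reproduces. Protocol 11.3 says that 330 was chosen for exposure to the device, so power did not set the size. The gain is unknown and could be close to nil. All of this stands, and it makes the point an improvement and not a correction.

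A reader might also infer more than the documents support:
- *That the model adjusts for baseline HbA1c alone.* It also includes centre as a random factor, and randomization is blocked by centre.
- *That the 0.3 correlation is built into the analysis.* It is a planning value. The fitted model uses whatever correlation is observed.
- *That the imbalance judgement is an open door to bias.* The person judging sees the distributions by arm but is unaware of outcome associations, and the judgement triggers only a sensitivity analysis. It cannot change the primary estimate.
- *That the judgement is made from the SAP 13 table.* Neither Protocol 11.5.2 nor SAP 8.4 says so.
- *That everyone who did the run-in was new to CGM, so prior use must predict the Control outcome.* Protocol 3.1 also sends to the run-in users of other CGMs and Dexcom G6 users with under 85% of readings. An effect of prior use is a reasonable expectation, but the documents do not measure it.
- *That 2:1 allocation makes chance imbalance a serious threat.* Against 150:150, the standard error of a covariate mean difference rises by a factor of √(0.015/0.01333) = 1.06.

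None of this shows that adding the three covariates would do harm.

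**Conclusion.** The point holds as an efficiency improvement. The planned primary analysis is valid and adequately described; a reading that it is underpowered or biased for want of these covariates is not supported. For an assumed partial R² from 0 to 0.20, the difference detectable at 90% power moves from 0.379 to somewhere between 0.379 and 0.339. Equivalently, 240 to 300 completers would do the work of 300.

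These figures rest on SD 1.0, r = 0.3, 200:100 completers and a common residual SD. A different SD rescales every detectable difference equally and leaves the proportional gain as it is. A higher r would improve the planned model without any change.

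The mismatch between SAP 13 and the eligibility criteria does not depend on any of these assumptions and should be corrected whatever is decided about the model.

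**What to change.** 1. Before unblinded outcome data are seen, prespecify in Protocol 11.6 and SAP 7 that the primary HbA1c model includes baseline HbA1c, baseline mean CGM glucose, pump versus injections, prior CGM use, and centre as a random factor.
2. Define the covariates: mean glucose over the SAP 5.3 baseline period, with a rule for participants lacking the minimum data; and prior CGM use from the enrollment record, not from whether the run-in was skipped.
3. Keep the model with baseline HbA1c and centre as a sensitivity analysis.
4. Record the change in SAP 2 as well as in Protocol 11.6.
5. Separately, change the insulin-method categories in SAP 13 to pump or injections.

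The cost is three extra terms in about 300 participants, the short definitions above, and a minor protocol amendment, which Protocol 13.2 requires the IRB to approve. No new data are needed.

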# 1. Study Overview

33 34 35

36

The following table gives an overview of the 2IQP study.

# 37 Table 1. Study Overview

PARTICIPANT AREA	DESCRIPTION				
Title	A Randomized Trial Evaluating the Efficacy and Safety of Control-IQ Technology in Adults with Type 2 Diabetes Using Basal-Bolus Insulin Therapy				
Précis	A randomized controlled trial (RCT) will evaluate 13 weeks of home use of the t:slim X2 insulin pump with Control-IQ technology in adults with type 2 diabetes age 18 and older using basal-bolus insulin therapy compared with continuation of pre-study insulin delivery plus continuous glucose monitoring (CGM). Exercise and meal-related challenges will be performed by all participants in the Control-IQ group unless there is a cardiac contraindication or other safety concern.				
Investigational Device	t:slim X2 insulin pump with Control-IQ technology v1.5 (Control-IQ System)				
Objectives	• To assess the safety of use of Control-IQ technology in adults with type 2 diabetes using basal-bolus insulin therapy				
	• To assess the efficacy of use of Control-IQ technology in adults with type 2 diabetes using basal-bolus insulin therapy				
	• To assess user satisfaction and quality of life with use of Control-IQ technology in adults with type 2 diabetes using basal-bolus insulin therapy				
Study Design	RCT				
Number of Sites	~20-25 clinical centers in the U.S. and Canada				
Key RCT Endpoints	Key Effectiveness Endpoints         These endpoints will be tested in the following hierarchy to control for the type I error         • HbA1c (primary)         • Time in range 70-180 mg/dL         • Mean glucose         • Time >180 mg/dL         • Prolonged hyperglycemia events (≥90 minutes >300 mg/dL within a 120-minute period)         • Time <70 mg/dL         • Time <54 mg/dL         • CGM-measured hypoglycemia events (15 or more consecutive minutes <54 mg/dL)         • Coefficient of variation         Calculation of CGM metrics for the treatment group comparison will exclude the challenge and the 24-hour period following the end of the challenge				
	Severe hypoglycemia				

PARTICIPANT AREA	DESCRIPTION				
	Diabetic ketoacidosis				
	Hyperosmolar hyperglycemic syndrome				
	• Other serious adverse events				
	Unanticipated adverse device effects				
	
 
Hypoglycemia and prolonged hyperglycemia endpoints listed as effectiveness endpoints
 
				
	• Infusion set failures				
	• Other device malfunctions/device issues				
	Other Endpoints				
	• % time in closed loop				
	• Total daily insulin delivery				
	• Weight change				
	Change in lipid levels				
	Cardiovascular events				
	Patient-reported outcome (PRO) measures				
	
 
Diabetes Distress Scale
 
				
	• Diabetes Impact and Device Satisfaction Scale				
	• PROMIS (Sleep Related Impairment Questionnaire)				
	
 
DAWN-Impact of Diabetes Profiles
 
				
	• HFS I and II				
	◦ EQ5D				
	• Study-specific survey				
	
 
System Usability Scale (SUS)
 
				
	Frequency of non-severe hypoglycemia				
	Exploratory analyses will evaluate endpoints in subgroups based on diabetic medication use, body mass index, baseline HbA1c				
Eligibility Criteria	Inclusion Criteria				
	1. Age $\geq 18$ years old at time of screening				
	2. Currently resides in the U.S. or Canada with the ability to complete in- person study visits at one of the participating clinical sites				
	
 
Clinical diagnosis, based on investigator assessment, of type 2 diabetes of at least 6 months duration at time of screening.
 
				
	4. Using basal-bolus insulin therapy with at least one injection containing rapid-acting insulin per day or an insulin pump for at least 3 months prior to enrollment, with no major modification to insulin regime in the last 3 months				
	• Mixed insulin with a rapid component is acceptable				
	5. If using noninsulin glucose-lowering medications (such as GLP-1 receptor agonist, SGLT2 inhibitor, or other) or weight-reduction medications, dose has been stable for the 3 months prior to screening; and participant is willing to not change the dose unless required for safety purposes				
	6. Participant willing to not initiate use of any new glucose-lowering medications during the trial				

PARTICIPANT AREA	DESCRIPTION				
	7. Willing to use an approved insulin while using the study pump if assigned				
	to the AID group				
	8. Willing to not use concentrated insulin above U-100 or inhaled insulin				
	Willing to participate in the study meal and everyise challenges if assigned				
	to the AID group, and have a care partner, trained in hypoglycemia				
	treatment guidelines, to include glucagon use, present during and				
	immediately after the exercise challenges.				
	10. Has the ability to read and understand written English				
	Investigator believes that the participant has the cognitive capacity to provide informed consent				
	12. Investigator believes that the participant can successfully and safely operate all study devices and is capable of adhering to the protocol and completing the study				
	13. No medical, psychiatric, or other conditions, or medications being taken that in the investigator's judgement would be a safety concern for participation in the study.				
	
 
This includes considering the potential impact of medical conditions
 
				
	known to be present including cardiovascular, liver, kidney disease,				
	thyroid disease, adrenal disease, malignancies, vision difficulties,				
	active proliferative retinopathy, and other medical conditions;				
	psychiatric conditions including eating disorders; drug or alcohol abuse.				
	14. Participants capable of becoming pregnant must meet one of the following criteria:				
	a. has a negative urine pregnancy test and agrees to use one of the accepted contraceptive regimens throughout the entire duration of the trial from screening until last follow-up visit. The following contraceptive measures are considered adequate:				
	i. Combined estrogen and progestogen containing hormonal contraception associated with inhibition of ovulation (oral, intravaginal, transdermal)				
	ii. Progestogen-only hormonal contraception associated with inhibition of ovulation (oral, injectable, implantable)				
	iii. Placement of an intrauterine device or intrauterine hormone-releasing system				
	iv. Bilateral tubal occlusion				
	v. Barrier methods of contraception (condom or occlusive cap with spermicidal foam/gel/film/cream/suppository).				
	vi. Has a vasectomized or sterile partner (where partner is sole partner of subject) and where vasectomy has been confirmed by medical assessment				
	vii. Exercises true sexual abstinence. Sexual abstinence is				
	defined as refraining from heterosexual intercourse during the entire period of risk associated with the study				
	treatments. The reliability of sexual abstinence needs to be evaluated in relation to the duration of the clinical				

PARTICIPANT AREA	DESCRIPTION					
	trial and the preferred and usual lifestyle of the subject.					
	or					
	b. Participant is of non-childbearing potential due to menopause with at least one year since last menses or a medical condition confirmed by the investigator					
	Exclusion Criteria					
	1. Current use of hybrid closed-loop system					
	2. Current use of systemic glucocorticoids or anticipated use of glucocorticoids during the RCT ( topical or inhaled -ie, non-systemic is acceptable ).					
	3. Current use of sulfonylurea or meglitinide medications					
	4. Current use of hydroxyurea					
	5. Tape allergy or skin condition that will preclude use of the study pump or CGM					
	6. Presence of a hemoglobinopathy or other condition that is expected to affect the measurement of HbA1c					
	
 
Pregnant (positive urine hCG), breast feeding, plan to become pregnant during the study period, or sexually active without use of accepted contraceptive measures
 
					
	8. Current participation in another diabetes-related interventional clinical trial					
	9. Anticipated change of residency or travel for more than 7 days at a time during the study that may, per investigator judgment, interfere with the completion of study visits, contacts, or procedures					
	10. Immediate family member (spouse, biological or legal guardian, child, sibling, parent) who is an investigative site personnel directly affiliated with this study or who is an employee of Tandem Diabetes Care, Inc.					
	Eligibility for Exercise Challenges					
	All participants will have a screening EKG or review of an EKG completed in the 12 months prior to screening.					
	To participate in the exercise challenge, a participant must not have a history of a cardiovascular event in the year prior to screening and/or EKG abnormalities associated with increased risk during exercise.					
Sample Size	A maximum of 450 individuals may be enrolled (consented for screening) in order to achieve the goal of 330 randomized participants.					
	This equates with a maximum of 220 using the AID system for 13 weeks and 110 using pre-study basal-bolus insulin delivery method plus the study CGM. Assuming 10% drop out rate in each group, there will be 200 using the system for 13 weeks.					
	Approximate Study Goals					
	- Minimum 25% MDI users					
	- Minimum 30% of a minority race or ethnicity					
	- Minimum 10% older than 50 years old					
	- Minimum 20% using an SGLT2 inhibitor,20% using a GLP-1 receptor agonist, and a minimum of 10% using both					

PARTICIPANT AREA	DESCRIPTION				
	
 
Minimum of 15% with TDI> 100 units/day and attempt to enrich cohort with participants with TDI >200 units
 
Minimum of 25% using a form of fixed dosing to calculate meal boluses (e.g., fixed dose at meal or fixed dose for small/medium/large meal [i.e., dose not determined by carbohydrate counting])
 
				
	- Maximum of 25% with HbA1c <8% (based on screening HbA1c of HbA1c available within the last 30 days) and maximum of 10% with screening HbA1c <7%				
Treatment Groups	Random assignment 2:1 to an intervention group or control group:				
	
 
Intervention group: t:slim X2 insulin pump with Control-IQ technology and Dexcom G6 CGM
 
				
	• Control group: Continuation of pre-study basal-bolus insulin delivery method, plus use of study CGM (Dexcom G6)				
Participant Duration	~13-17 weeks, depending on duration of run-in phase				
Study Duration (planned)	~9 months from first enrollment until last participant visit (assuming 4-month recruitment period; study duration will be extended as needed to complete recruitment)				
Protocol Overview/Synopsis	Screening Visit				
	• Informed consent obtained and participant screened for eligibility. Testing for eligibility assessment and baseline will include:				
	
 
Medical history, including total daily insulin dose, prior severe hypoglycemia, diabetic ketoacidosis (DKA), hyperosmolar hyperglycemic syndrome (HHS), and hospitalizations for these events.
 
				
	
 
HbA1c with point-of-care device or local lab, unless available from the prior 30 days
 
				
	
 
Focused physical exam, including height and weight to compute body mass index (BMI) and blood pressure
 
				
	
 
Urine pregnancy test for participants capable of becoming pregnant
 
				
	• EKG unless performed within 12 months prior to screening				
	• Subjective Numeracy Scale				
	including frequency of non-severe hypoglycemia during the prior 3 months				
	CGM Run-in				
	• Eligible participants will be started on the study CGM, if applicable				
	• Experienced current users of the study CGM with at least 85% of available readings from prior 14 days will skip the CGM Run-In				
	• Otherwise, participants will use CGM for a minimum of 21 days				
	
 
Training provided to use the CGM in conjunction with basal- bolus insulin therapy
 
				
	
 
Participants expected to use the CGM until return for post- run-in clinic visit.
 
				

PARTICIPANT AREA	DESCRIPTION				
	
 
At investigator discretion, contacts may occur with participant during run-in phase for further training on use of CGM
 
Participants will continue use of their personal insulin delivery method (nump or MDI)
 
				
	Clinic visit after 21-28 days				
	
 
Participant must have used CGM for at least 85% of the time during the most recent 14 days. If this requirement is not met, the run-in phase can be extended for an additional 14-21 days at the investigator's discretion.
 
The most recent 14 days of CGM data will be used as the baseline for
 
				
	analyses				
	
 
For participants completing the CGM Run-in, Randomization Visit typically occurs on same day as End of Run-in Visit; if participant is not ready to start the AID system if randomly assigned to the intervention group, it must occur within 14 days after completion of the run-in phase. For participants skipping the CGM Run-in, Randomization Visit may occur on same day as Screening Visit (so long as all eligibility criteria have been verified) or within 14 days following the Screening Visit.
 
				
	• If not on same day as Screening Visit,				
	
 
Solicit any changes in medical conditions since screening that could affect eligibility for the RCT
 
				
	• Vital signs				
	
 
Urine pregnancy test for participants capable of becoming pregnant
 
				
	• Blood draw for central lab measurement of HbA1c, lipids, creatinine, C-peptide, glucose, and GAD antibodies				
	Randomization to the AID group or Control group				
	• AID group: Initiation of AID system and training on its use (initial training typically will be completed and AID system use initiated on day of randomization but if investigator does not believe that participant is ready to start the study pump, initiation of the study pump can be deferred for further training, but initiation of the AID system must occur within 7 days of randomization). Insulin aspart will be provided for participants who prefer to use the study insulin.				
	
 
Control group: Training on use of study CGM and continuing pre-study basal-bolus insulin therapy
 
				
	13-week RCT protocol				
	• Participants in AID group will have a contact 3 ±1 days after initiation of closed loop (may coincide with 7-day visit) for further review of training materials and to answer questions. Participants will be specifically instructed to contact the site for any issues that arise during the first infusion set change.				
	• Participants in AID group will be expected to use the system continuously until the 13-week visit (unless a condition occurs, such as illness, in which the participant is instructed by the site to temporarily switch to open-loop)				
	• Addition of glucose-lowering or weight reduction medications or dose changes in such medications in use at the time of randomization are				

PARTICIPANT AREA	DESCRIPTION				
	prohibited during the 13 weeks of the RCT, unless determined by the				
	investigator to be necessary for safety.				
	
 
If a participant in the AID group has a change in dose or addition of a new glucose-lowering or weight-reduction medication, an unscheduled visit will occur after 1-2 days and ~7 days to assess safety.
 
				
	• Instructions will be provided for when to test for ketones and management when ketosis is present (see section 4.6.4)				
	• Participants will not be restricted on diet or exercise.				
	• Participants in the Control group will be expected to use CGM on daily basis.				
	RCT Visits and Contacts				
	• As noted earlier, the AID group will have a contact 3 ±1 days after initiating the AID system to address any questions after initial use of the AID system and further training as needed.				
	• For both groups, in-clinic visits will occur 4 weeks ± 4 days and 13 weeks ± 4 days; and a remote (phone or video) visit will occur after 7±2 days for a safety check. An additional clinic visit or contact will occur after 8 weeks ± 4 days (depending on whether participant is able to upload device data at home and whether investigator believes clinic visit is needed).				
	At each scheduled visit/contact:				
	• Review medications and doses				
	• AID system and CGM data will be reviewed (participants without the ability to upload the device data from home will be provided with a laptop to use during the study)				
	
 
Site investigators may adjust insulin delivery profile settings ONLY for safety concerns and will document reasons for change in the CRF
 
				
	• Occurrence of adverse events will be solicited				
	• Assessment of TDD over last week				
